FULL/LONG TITLE OF THE STUDY

Online Psychological Treatment for People with Painful HIV-related Peripheral Neuropathy (OPEN Study): Qualitative Investigation of Treatment Needs

NCT02972606

SHORT STUDY TITLE / ACRONYM

OPEN Study: Pain management treatment needs interviews

PROTOCOL VERSION NUMBER AND DATE

- Protocol version 5.0 24 April 2017
- **This protocol has regard for the HRA guidance and order of content**

RESEARCH REFERENCE NUMBERS

IRAS Number: 205949

SPONSORS Number: Not Applicable

FUNDERS Number: PDF-2015-08-059

SIGNATURE PAGE

The undersigned confirm that the following protocol has been agreed and accepted and that the Chief Investigator agrees to conduct the study in compliance with the approved protocol and will adhere to the principles outlined in the Declaration of Helsinki, the Sponsor's SOPs, and other regulatory requirement.

I agree to ensure that the confidential information contained in this document will not be used for any other purpose other than the evaluation or conduct of the investigation without the prior written consent of the Sponsor

I also confirm that I will make the findings of the study publically available through publication or other dissemination tools without any unnecessary delay and that an honest accurate and transparent account of the study will be given; and that any discrepancies from the study as planned in this protocol will be explained.

Chief Investigator:

Signature:

Date:

24/04/2017

Name: (please print): [name]

KEY STUDY CONTACTS

Chief Investigator	[name] [name] [contact]
Sponsor	[name] Director of Research Management and Innovation King's College London [name] [contact] Email: [contact]
Joint-sponsor(s)/co-sponsor(s)	Not applicable.
Funder(s)	National Institute for Health Research
Key Protocol Contributors	[name] [name] [name]
Committees	Not applicable.

STUDY SUMMARY

Study Title	Online Psychological Treatment for People with Painful HIV-related Peripheral Neuropathy (OPEN Study): Qualitative Investigation of Treatment Needs
Internal ref. no. (or short title)	OPEN Study: Pain management treatment needs interviews
Study Design	Qualitative Semi-Structured Interviews
Study Participants	Individuals living with HIV and chronic painful peripheral sensory neuropathy.
Planned Size of Sample (if applicable)	Approximately 30 participants.
Follow up duration (if applicable)	Not applicable.
Planned Study Period	November 2016 to August 2017
Research Question/Aim(s)	To investigate the needs of people with HIV and painful sensory neuropathy for a psychological treatment to reduce the impact of pain on quality of life. To explore the acceptability of an internet-delivered psychological intervention and to tailor the content and delivery format of the intervention to the identified needs of this group.

FUNDING AND SUPPORT IN KIND

FUNDER(S)	FINANCIAL AND NON FINANCIAL SUPPORT GIVEN
(Names and contact details of ALL organisations providing funding and/or support in kind for this study)	
National Institute for Health Research	Financial (salary costs of the CI, and training and research costs)

ROLE OF STUDY SPONSOR AND FUNDER

The lead sponsor, King's College London, will take primary responsibility for ensuring that the design of the study meets appropriate standards and that arrangements are in place to ensure appropriate conduct and reporting. King's College London also provides cover under its No Fault Compensation Insurance, which provides for payment of damages or compensation in respect of any claim made by a research subject for bodily injury arising out of participation in a clinical trial or healthy volunteer study (with certain restrictions).

The funder reviewed and approved the study in the process of the Chief Investigator's fellowship application. The Chief investigator must notify the funder of any publication at the time of submission or at least 28 days prior to publication.

ROLES AND RESPONSIBILITIES OF STUDY MANAGEMENT COMMITTEES/GROUPS & INDIVIDUALS

The study steering group will consist of [name], [name], [name], [name], and two patient representatives, [name] and [name]. The steering group will ensure that the study adheres to the protocol, and meets recruitment, data analysis, and dissemination objectives. [name] will oversee the day-to-day management of the study.

Protocol contributors

[name] drafted the protocol in collaboration with Professors [name] and [name], and [name]. Two patient representatives ([name] and [name]) provided input on the recruitment strategy, questionnaires and interview schedule, and participant information sheet and consent form. Another HIV patient organization (UKCAB) provided feedback on patient-facing study documents.

KEY WORDS:

HIV, pain, peripheral neuropathy, psychological treatment, qualitative research

LIST of CONTENTS

GENERAL INFORMATION	Page No.
TITLE PAGE	1
RESEARCH REFERENCE NUMBERS	2
SIGNATURE PAGE	3
KEY STUDY CONTACTS	4
STUDY SUMMARY	5
FUNDING	6
ROLE OF SPONSOR AND FUNDER	7
ROLES & RESPONSIBILITIES OF STUDY STEERING GROUPS AND INDIVIDUALS	8
LIST of CONTENTS	9
STUDY FLOW CHART	10
SECTION	
1. BACKGROUND	11-12
2. RATIONALE	11-12
3. THEORETICAL FRAMEWORK	12
4. RESEARCH QUESTION/AIM(S)	12
5. STUDY DESIGN/METHODS	13-14
6. STUDY SETTING	15
7. SAMPLE AND RECRUITMENT	15-17
8. ETHICAL AND REGULATORY COMPLIANCE	17-20
9. DISSEMINATION POLICY	20
10. REFERENCES	21-23
11. APPENDICES	N/A

STUDY FLOW CHART

Table 1. Timeline of Study Activities

Month	Nov '16	Dec '16	Jan '17	Feb '17	Mar '17	Apr '17	May '17	Jun '17	July '17	Aug '17	Sept '17
Recruitment/ screening	X	X	X	X	X	X	X	X	X		
Informed consent, questionnaire and interview completion	X	X	X	X	X	X	X	X	X		
Transcribing	X	X	X	X	X	X	X	X	X	X	
Data Analysis	X	X	X	X	X	X	X	X	X	X	
Dissemination									X	X	X

STUDY PROTOCOL

OPEN Study: Pain management treatment needs interview

1 and 2: BACKGROUND and RATIONALE

The human immunodeficiency virus (HIV) remains a significant global health concern. An estimated 35 million people are infected with HIV worldwide (1, 2); approximately 110,000 infected individuals are in the United Kingdom (3). Antiretroviral therapies have significantly improved survival rates. At the same time, approximately 6,000 individuals are newly infected with HIV in the UK each year (3). Consequently, the prevalence of infected individuals is growing.

In well-resourced countries, the shift in HIV from a terminal illness to a chronic condition has contributed to a greater focus on disease and symptom management (4). Pain in the feet is one of the most predominant symptoms associated with HIV infection and treatment. Approximately 40 to 60% of people with HIV have peripheral sensory neuropathy (HIV-SN); 50-90% of these experience neuropathic pain (5-7).

Painful HIV-SN is associated with increased disability in daily activities, unemployment, and reduced quality of life (8). Additionally, painful HIV-SN is associated with numerous comorbidities, including depression, panic disorder, post-traumatic stress disorder, and substance abuse (9-13). Thus, untreated painful HIV-SN may contribute to significant individual, societal, and economic burden.

Presently, there are few options for medically managing painful HIV-SN. A systematic review of 19 randomized controlled trials (RCTs) of pharmacological treatments for painful HIV-SN indicated that efficacy was found only for topical capsaicin, smoked cannabis, and subcutaneous nerve growth factor; however, only capsaicin is clinically feasible (14). Additional negative RCTs of pregabalin and capsaicin have since been published (15, 16). It has been concluded that there is an 'urgent need' to evaluate novel strategies to manage painful HIV-SN (14).

Psychological treatments, including Cognitive Behavioural Therapy (CBT), represent a potentially viable addition to the treatment of painful HIV-SN. In meta-analyses, CBT is associated with improved pain, function, and depression among individuals with chronic pain that is primarily musculoskeletal in origin (17). The development of accessible and cost-effective Internet-administrations of CBT for pain is another promising development in this area (18).

Within the broad category of CBT, Acceptance and Commitment Therapy (ACT) is a more recent treatment technology with growing support for individuals with chronic musculoskeletal pain. There are now 11 RCTs and numerous effectiveness studies supporting the efficacy and effectiveness of ACT for long-term improvements in pain, function, distress, and healthcare utilization (19, 20). ACT is a particularly promising innovation given its explicit theoretical basis—the psychological flexibility model. This model provides a unifying framework for targeting processes of change, evaluating treatment mechanisms and, ultimately, refining treatment (21). Additionally, the psychological

flexibility model and ACT are transdiagnostic, with applicability and demonstrated efficacy across a wide range of health conditions (22-24). Indeed, preliminary findings suggest an association between pain acceptance and improved HIV-related pain outcomes (25).

Despite advancements in research on CBT and ACT for musculoskeletal pain conditions, comparable research does not exist for individuals with painful HIV-SN. One systematic review of CBT for neuropathic pain identified only 3 RCTs (26). Only one of these RCTs focussed on HIV-related pain; this study had an unacceptably high dropout rate of 57% (27). Two additional observational cohort studies of group-based CBT for HIV-related pain showed similarly poor adherence (28, 29). There is a clear need for improving psychological interventions for individuals with HIV-related pain. Patient representatives and clinicians practicing in the area of HIV and pain management have been consulted with respect to this issue and have identified the need for better development and implementation of psychological treatments for pain in this population.

Improving psychological treatments for painful HIV-SN will likely require greater consideration of the psychosocial complexities associated with this condition. For example, HIV is most common among gay men, women, ethnic minorities, and intravenous drug users (3, 30). There is recognition of important healthcare disparities and under treatment of pain in these groups (31-33). However, the unique perspectives and needs of individuals in these groups are not typically incorporated into psychologically-based pain management interventions such as CBT/ACT. Moreover, findings from the available qualitative literature suggest that social stigma and interpersonal distrust may influence treatment engagement among individuals with HIV (34-38). However, research is needed to understand how these psychosocial issues can best be addressed within CBT/ACT for pain.

This study will use in-depth interviews to examine the needs of people with painful HIV-SN for a psychologically-based pain management treatment that may be delivered over the Internet. Interview questions will examine the impact of pain on people's lives and how they cope with pain, and participants' treatment needs in terms of treatment content and delivery format. Men, women, ethnic minorities, and people who use recreational drugs will be purposively sampled to ensure that interview responses reflect the views of people most commonly suffering from this condition.

3 THEORETICAL FRAMEWORK

Broadly speaking, the study is framed within a biopsychosocial understanding of the experience of chronic pain. The purpose of the study is to understand, from the perspective of people living with HIV-related painful peripheral neuropathy, people's needs for and views about a psychological approach to pain management delivered over the internet. As such, data collection and analysis will follow a grounded theory approach. Following this approach, meanings and themes that emerge from the interviews will be used to develop a conceptual understanding of participants' experiences of pain and their views about a new pain management intervention.

4 RESEARCH QUESTION/AIM(S)

4.1 Objectives

The purpose of this study is to explore the needs of people with painful HIV-SN for a psychologically-based treatment for managing chronic pain.

4.2 Outcome

The interview responses will be used to develop and tailor an internet-delivered version of ACT for people with painful HIV-SN. Once developed, the new treatment will be tested in a feasibility trial (another study). It is hoped that tailoring the online ACT treatment based on the qualitative interview responses will increase the acceptability of the treatment and will improve treatment adherence rates.

5 STUDY DESIGN and METHODS of DATA COLLECTION AND DATA ANALYSIS

Participants will complete semi-structured interviews. Prior to the in-depth interview, participants will complete a questionnaire package at home to bring to their interview appointment (20-30 minutes to complete). The questionnaire package will consist of demographic and medical history questions, and symptom and functioning questionnaires. Individual in-depth semi-structured interviews will be conducted given the potentially sensitive nature of the questions and to maintain participants' anonymity. Participants will be given the choice to complete the interviews at the Imperial College London campus of Chelsea & Westminster Hospital or Guy's Hospital Campus of King's College London, according to their preference.

At the beginning of the interview appointment, the interviewer will conduct a 5 minute clinical examination to assess of symptoms and signs related to peripheral neuropathy. In the event that questionnaires are not completed prior to the interview session, participants will be asked to complete the questions at the interview appointment or at home and to mail them back in within 2 weeks. Participants who have not completed the questionnaires 3 weeks after the interview will receive a telephone reminder.

Pre-Interview Questionnaires

Demographic, Medical History, and Internet Use Questions: Participants will be asked to report on the following demographic and medical history questions: age, gender, ethnicity, sexual orientation, education, employment status, living situation, date of HIV diagnosis, history of and current antiretroviral treatment, duration of foot pain, other chronic pain diagnoses, mental health diagnoses, current pain medications, current alcohol and drug use, and frequency of Internet use.

Pain intensity and interference: The Brief Pain Inventory (BPI) will be used to assess pain intensity and the interference of pain with daily functioning in seven domains: general activity, mood,

walkingability, relations with others, sleep and enjoyment of life. The BPI has been shown to be a reliable and valid measure for use with people with neuropathic pain conditions, including peripheral neuropathy (39). Participants will also be asked to fill in a body map to indicate where they feel pain.

Neuropathic Pain Interview: The 7-item DN4-i (Douleur Neuropathique 4-interview, English version) interview (questionnaire version) will be conducted to identify the probability that the participant has neuropathic pain. A score of ≥ 3 out of 7 reflects a positive diagnosis of neuropathic pain (40) (41).

Patient Health Questionnaire (PHQ-9): The PHQ-9 (42) is a 10-item measure of the severity of depression symptoms based on the DSM-IV diagnostic criteria for depression. Each item is rated on a four point scale between 0 (not at all) and 3 (nearly every day). The PHQ-9 has shown reliability and validity as a measure of depressive symptoms and is commonly used as an outcome measure in studies of patients with chronic pain (42).

Interview Appointment

Assessment of neuropathy signs and symptoms

The Clinical HIV-associated Neuropathy Tool screening tool (12) will be administered at the beginning of the interview appointment (5 minutes). This 4-item tool comprises two subjective symptom questions (self-report of foot pain and foot numbness), and two objective signs on clinical examination (loss of vibration sense and loss of ankle reflex). Clinical examination of these signs does not require specialist medical training. Based on a previous study using the CHANT, patients are considered to have peripheral neuropathy if they are positive for one symptom and one sign in a bilateral distribution (43). Previous data indicate that the CHANT has 100% sensitivity and 85% specificity for diagnosing HIV-SN in a London-based sample in relation to a more comprehensive neurological examination (The Utah Early Neuropathy Score) as the reference standard (43). Information from the physical examination of the CHANT will be used to further support the case definition of peripheral neuropathy from the telephone screening. However, findings of positive signs from the physical examination are not a requirement for study inclusion and all participants will proceed to the semi-structured interview.

Semi-structured interview

The interview schedule was developed on the basis of previous qualitative studies on psychological factors and treatments for pain in general and specifically in people with HIV (44, 45) and online CBT for pain management (46), and patient input. Participants will first be asked general questions about the impact of pain on their lives and how they currently cope with pain. They will also be asked more specific questions about their thoughts about an online psychological treatment for managing pain. While an interview schedule has been developed for the study, we expect questions to be further developed and revised during the study as data and themes emerge that require further probing.

[name] will conduct the interviews, which are expected to take approximately 1 hour each. Field notes will be made during/immediately after the interview to record the interviewer's impression of the participant's responses and the interview process. All interviews will be recorded using a dictaphone, transferred to a password-protected computer, and anonymised by [name]. [name] and a Bachelor's level (or higher) student or volunteer will transcribe the anonymized audio recordings verbatim.

Thematic analysis will be used to analyse the data following the recommendations of Braun and Clark (2006): Each transcript will be read in its entirety several times to establish familiarity. First level-descriptive codes will be annotated in the margin of the transcript. Second level codes will be used to summarize the most significant/frequent first-level codes; third-level codes will be used to identify higher order themes around which lower order themes are integrated. Quotes reflecting second-level themes will be extracted to demonstrate second-level themes for the final report (47). The NVivo 11.0 software program will be used to assist in data analysis. This process will be initially conducted by one coder; two additional coders will code 10% of the transcripts to establish the validity of the codes. Validity will also be established through use of the constant comparative method whereby the transcripts will repeatedly be reviewed to check that identified 2nd and 3rd level themes correspond to the data.

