7.2.2 Consent

Following screening, the study coordinator will review the participant information sheet with eligible participants either in person or over the telephone to describe the nature and objectives of the study and possible risks. Potential participants will be given the opportunity to ask the researcher any questions at this time. Potential participants will be given up to 1 month to consider the information and to decide whether they want to participate or not. Eligible individuals will be mailed a copy of the information sheet along with two copies of the consent form, and the pre-interview

questionnaires. Participants will be asked to bring the completed consent form to their interview appointment. The right to refuse to participate without giving a reason will be respected. We will emphasize that participants are free to withdraw at any time without consequence.

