8 ETHICAL AND REGULATORY CONSIDERATIONS

8.1 Assessment and management of risk

Participants' involvement in the study will contribute to further developments in psychological treatments for people with painful HIV-related peripheral neuropathy. Participants will receive a gift voucher as compensation for their time. We cannot guarantee any further benefits to participants for their involvement in the study.

Adverse events arising from this observational study are expected to be rare. However, it is possible that participants could become distressed in the course of the interview given the potentially sensitive nature of the questions. [name] will debrief participants about any distress that comes up in the interviews. The interviewer, [name], is a registered clinical psychologist and will remain sensitive to this issue. All participants will be informed of their right to stop the interview at any time and that information will be kept strictly confidential. Participants can request to withdraw parts or all of their data.

We will write a letter to the GP to inform him/her of the participant's involvement in the study. Participants who score 10-14 on the PHQ-9 will be made aware of their score and will be recommended to contact their GP if they are concerned about this. Participants who score 15 or greater on the PHQ-9 will be informed of this, and will be told that [name] will directly contact their GP to discuss this. A similar procedure will be followed if we discover any other symptoms that might pose a risk to a participant's health or well-being during the course of the interview appointment.

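### The PHQ-9 may be posted back after the interview, which delays or loses the score-based GP step in section 8.1 for participants who use that route

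*Combined protocol and SAP*

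**What the plan says.** Section 5 sets the default route: "participants will complete a questionnaire package at home to bring to their interview appointment (20-30 minutes to complete"). Section 7.2.2 (Consent) explains how the forms reach people: "Eligible individuals will be mailed a copy of the information sheet along with two copies of the consent form, and the pre-interview" questionnaires. The PHQ-9 is described in section 5 under the pre-interview questionnaires, so the return rule for the package applies to it.

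For a package that has not been completed beforehand, section 5 says that "participants will be asked to complete the questions at the interview appointment or at home and to mail them back in within 2 weeks". It states no preference between the two options and makes no exception for the PHQ-9. The only follow-up is this: "Participants who have not completed the questionnaires 3 weeks after the interview will receive a telephone reminder".

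Section 8.1 attaches actions to the score. In the lower band, "Participants who score 10-14 on the PHQ-9 will be made aware of their score and will be recommended to contact their GP", subject to the participant being concerned about it. In the upper band, "Participants who score 15 or greater on the PHQ-9 will be informed of this" and told that the study team will contact the GP directly. Section 8.1 also provides that the interviewer, a registered clinical psychologist, debriefs distress arising in the interview. Comparable steps apply to other risk symptoms found at the appointment, and a routine letter tells the GP that the patient is taking part.

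**The concern.** The PHQ-9 does two jobs in this protocol. Section 5 presents it as a symptom measure that "has shown reliability and validity as a measure of depressive symptoms", and for that purpose late return matters little. Section 8.1 also makes it the trigger for telling the participant and contacting the GP, and for that purpose timing matters. The return rule in section 5 fits the first job only.

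The stake is individual patient safety. The background section lists depression among the comorbidities of painful HIV-SN, and section 8.1 defines two action bands, so scores in those bands are foreseeable. A participant who would score 15 or more, takes the form home, and shows or mentions nothing worrying at the appointment leaves without the GP contact that the protocol intends for that score. Yet that participant has just spent about an hour with a clinical psychologist, at a visit where the form could have been completed.

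**Working it through.** The plan gives no figure to reproduce. The check sets the return rule in section 5 beside the action rule in section 8.1 and follows each route, counting days from the interview. Section 5 does not say when its 2-week period starts; I assume it starts at the interview. Time in the post is not counted.

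**Inputs**
- Posting deadline (section 5): 2 weeks = 2 × 7 = 14 days.
- Telephone reminder (section 5): 3 weeks = 3 × 7 = 21 days after the interview.
- Interval from deadline to reminder: 21 − 14 = 7 days.
- Planned sample (section 7.2.1): about 30.

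**Earliest point at which the score-based step can start**

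| Route | Days after the interview |
|---|---|
| Brought completed, or completed at the appointment, and scored there | 0 |
| Posted on time | up to 14 |
| Posted late, before the reminder | 15 to 20 |
| Returned only after the reminder | 21 or more, no upper limit stated |
| Never returned | no score, so no score-based action |

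The zero in the first row is conditional. The protocol does not say that forms in hand are scored that day, and section 8.1 gives no time limit for acting on a score by any route.

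**Do the other safeguards replace the score?**
- The debrief responds to distress that surfaces in the interview.
- The provision for other risk symptoms responds to what is discovered at the appointment.
- Both therefore depend on what the participant shows or says. On the interview's content, section 5 states: "Participants will first be asked general questions about the impact of pain on their lives and how they currently cope with pain". Views on an online treatment follow. Mood may come up but is not a stated topic.
- Self-reported mental health diagnoses are part of the same package, so if the whole package is missing the interviewer lacks that information too.
- The GP letter is described only as telling the GP about participation.

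None of these supplies the score or depends on it, so they reduce the gap without closing it.

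**Number affected.** The documents give neither the share who would post the form nor the share scoring 10 or more, so no estimate is possible. One participant is 1/30 = 3.3% of the planned sample, which only restates the sample size.

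**The case against.** The strongest reply is that nothing here contradicts anything else. Section 8.1 says what happens when a score exists; it does not promise that everyone is screened. Participants may refuse without giving a reason and may withdraw parts of their data, so not returning a form is within their rights. This is a single-visit interview study with no treatment under test. That stands: the point is a design choice that can be improved, not an error.

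The day counts can also be challenged. Someone who completes the form at home on day 13 discloses on day 13, so the lag from disclosure to receipt is short. The default route has an uncounted lag of its own: forms are mailed ahead, people have up to 1 month to decide, and a form brought to the visit may be some time old. This is fair. The table measures time from the interview, the one occasion when the participant is certain to be with the clinician; it does not measure time from disclosure.

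The 10-14 action is only advice to contact the GP if concerned, so a short delay there matters little. That also stands, and the weight of the point rests on the band of 15 or more.

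Finally, the interview schedule is not reproduced and may probe mood more than section 5's summary suggests. That is possible, but cover that depends on what is said in an interview is still not the same as a score. The person affected must also arrive without the form, not complete it on site, score in an action band and show nothing at the visit, so the number is probably small. None of this removes the gap for a participant scoring 15 or more whose form is late or never returned.

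**Conclusion.** The concern holds, as a low-severity point worth acting on because the remedy is cheap. As written, the plan allows the score-based step to start up to 14 days after the interview for forms posted on time and 21 days or more after it for forms returned following the reminder. For forms never returned, the step does not occur. This rests on three things: the PHQ-9 falls under the package's return rule, as its place in section 5 indicates; the 2 weeks run from the interview; and no operating procedure outside the documents already requires scoring on site. It applies only to participants who use the postal route and only to the score-based step. How many they are cannot be estimated from the documents.

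**What to change.** Change the rule for the PHQ-9 only; the other questionnaires may still be posted.

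1. A participant who arrives without a completed PHQ-9 is asked to complete it at the appointment, before or after the interview as they prefer.
2. Every PHQ-9 in hand is scored before the participant leaves, and the section 8.1 action is taken then. This also covers forms brought from home.
3. If a participant declines on site, a form that arrives later is scored on receipt by the person who holds the anonymization log, because questionnaires carry only a study number (sections 8.7 and 8.10). The section 8.1 action follows within a stated limit, for example 2 working days.

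The cost is protocol wording, a few minutes of appointment time for those who arrive without the form, and slightly less choice about where to complete it. A mood questionnaire would sit close to a sensitive interview, which the choice of before or after eases. No extra staff are needed. A form declined on site and never returned would remain possible but should be less common.
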